Round Play- upon verification, players will be redirected to a series of instructional screens (See Appendix C) that reviews how LezParlay works and explain that points are won and lost by placing bets on your perceptions of the behaviors and attitudes of the typical LBQ woman in your age-group. In each round there will be between 1 and 3 question topics and each topic will contain approximately 8 questions. Four questions will ask you to report your own topic-specific behaviors or attitudes and the other four will ask you to guess about how other players in your age-group answered the same questions. For each guess you will be prompted to select the number of points you would like to bet on your guess being correct based on the average responses of other players. Screens will also inform participants that there is a variable cash prize between \$100 and \$500 in each round that will be awarded to the player who accumulates the largest number of points in that round. There are also grand prizes (\$1000, \$500, and \$250) that will be awarded to the top 3 scorers in each age-group who accumulate the largest numbers of points across rounds of play. A final screen will explain that after a critical mass (N=300+) in each age-group has played a round, LezParlay will text and email all players with a private link to an overview of the points won and lost along with detailed results on one topic. Detailed results are intended to help players improve the accuracy of their perceptions and place smarter bets in future rounds, as question topics may be repeated. Following this overview, a button will allow players to begin round 1.

The first screen in the round will reveal 2-3 question topics and the amount of the cash prize for the round's top scorer. Players will report their own answers to the questions then guess and bet points

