(i.e., 10, 25, or 50 points) on how other players will answer. Upon placing their bets, a final screen will reiterate that results will be sent out when a critical mass has played in their age-group. Additionally, they will be informed that they can help speed this along by inviting friends to play by sharing their personalized referral link, displayed below and also available in their account tab. When a critical mass has played (>300 in each age-group which we expect to take approximately 3 weeks), average responses to questions have been computed, and points won and lost have been calculated, links to view detailed results will be sent to players via text message and email. Clicking the private url will take the player to a spinner screen which displays their total score and reveals their detailed results topic initial “RESULTS LOADING” screen which summarizes the number of players in the users’ age-group who played the round to generate the correct answers (i.e., actual norms). Consistent with co-presence features in popular social media and digital apps, this summary consists of an animated collage displays the thumbnail avatars of all the players who completed the round. Recent studies in our lab have established that showing participants the peers on whom actual norms are based through such a collage increases the believability and credibility of the actual norms to be presented on subsequent feedback screens. The next screen encountered when viewing one’s detailed results will feature 3 animated graphical doors and instructions to select (tap or click) 2 of the doors in order to reveal either bonus points or topics on which detailed results will be delivered. For each question topic revealed by the door selection mechanic, personalized normative feedback (PNF) for each question will follow. PNF consists of bar charts with bars respectively representing 1) the participant’s guess about how other players answered (i.e., perceived peer norm); 2) the participant’s own answer to the question; and, 3) the actual average answer submitted by other players (i.e., actual peer norm). Text on each PNF screen will highlight an interesting statistic related to the actual norm and detail the number of points won/lost based on the accuracy of the player’s guess. Following PNF screens, participants will be presented with their total score and their age-group’s leaderboard which also crowns the winner of the round’s cash prize. The round winner will also be notified by email and text message and have the option of receiving their Visa gift card electronically or through the mail. See Appendix B for mockups of app screens.

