Qualtrics Research Suite's automated randomizer will be used to randomize evaluation study participants to a PNF condition at the point of study enrollment in round 3. Randomization will determine the sequence of topics on which participants will receive detailed results across intervention rounds 3 and 4: alcohol+coping, alcohol+control, or control only. Members of the research team will be blinded to participant condition assignment, and the study participants will not be aware that any sort of randomization was taking place. Rather, like in other rounds, when detailed results are sent players will be prompted to choose among 3 animated, graphical doors to determine the topics on which they will view detailed results. Although the results topics will be truly determined via chance in most rounds of the competition, the doors of evaluation study participants will be fixed to open to their randomly assigned feedback topics regardless of the door they selected in rounds 3 and 4. Upon completing the feedback survey at the end of the competition, participants will be debriefed regarding the study's research questions and the fixed sequences of health or control feedback they were randomized to receive in rounds 3 and 4. See Appendix D for the Debriefing Statement.

Replay Bonus Rounds 7 and 8.

The last 2 rounds of the competition, 7 & 8, will feature new question topics as well as previously assessed REPLAY BONUS topics which will allow all players to boost their scores by placing very large bets on a topic they already received feedback on and very small bets for topic on which feedback has not yet been delivered. PNF will be delivered for the new topics assessed in each round but will not be repeated for REPLAY BONUS topics. Instead a single screen will reveal the points earned from REPLAY BONUSES. Importantly, answers to REPLAY BONUS questions in Round 7 among intervention study participants' will act as the 2 month post-intervention follow-up for the purpose of the evaluation study RCT.

Competition Conclusion

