APPENDIX C

Norm questions to be featured in intervention rounds or potentially featured as control/filler questions in LezParlay Rounds

- Parallel Questions will also ask participants to report their own corresponding behavior/attitude/experience
- All questions will pipe the sexual identity (lesbian, bisexual, queer) and age-group (20s, 30s, 40s, 50s) of the user
- Some question topics and questions to appear in rounds will be voted on by players.
- Players can also submit their own questions to be voted on and potentially featured in some rounds.
- If any top voted user-submitted materially differ from those submitted in this exhaustive potential question list, we will submit an addendum to the IRB and get approval before any are featured in a round.

Alcohol Use Questions (Round 3 & Replay Bonus in Round 7)

During the past 2 months, on average, how many days per week did the Typical Lesbian drink alcohol?

- 0
- 1
- 2
- 3
- 4
- 5
- 6
- 7

During the past 2 months, on average, how many drinks did the Typical Lesbian have each time she drank?

- 0
- 1
- 2
- 3
- 4
- 5
- 6
- 7
- 8
- 9

10 or more

On the day she drank the MOST during the past 2 months, how many drinks did the Typical Lesbian have?

0

1

2

3

4

5

6

7

8

9

10

11

12 or more

HAD A HANGOVER OR ILLNESS

HAD PROBLEMS WITH FRIENDS OR FAMILY

GOT IN A PHYSICAL OR VERBAL FIGHT

PERFORMED POORLY AT WORK/SCHOOL

HAD PROBLEMS WITH GF/PARTNER

HAD PROBLEMS WITH MONEY

MISSED A SOCIAL ENGAGEMENT OR
EVENT

HAD AN UNWANTED OR REGRETTABLE
SEXUAL EXPERIENCE

During the past 2 months, how many of the 8 things above has the typical lesbian experienced due to drinking/partying?

0

1

2

3

4

5

6

7

Stigma Questions (Round 3 & Replay Bonus in Round 7)

During the past 2 months, what % of lesbians have been physically assaulted due to their sexual identity?
0% ----- 100%

During the past 2 months, what % of lesbians have been verbally harassed or threatened online or in person due to their sexual identity?
0% ----- 100%

During the past 2 months, what % of lesbians have overheard negative LGBTQ-related comments, jokes, or slurs?
0% ----- 100%

During the past 2 months, what % of lesbians have felt unwelcome or uncomfortable in a public place (gym locker room, store, restaurant, etc., due to their sexual identity?
0% ----- 100%

Coping Behaviors (Round 4)

When experiencing stress & stigma during the past month, what % of the time did the typical lesbian cope by drinking alcohol?
0% ----- 100%

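### If the app ties Round 7 Replay Bonus stakes to prior feedback, the only documented follow-up of perceived alcohol norms is taken under stakes that differ by randomized arm

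*Protocol*

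**What the plan says.** Four parts of the protocol bear on this point.

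- **Stake.** In ordinary rounds (section 3, Round Play) the player chooses: "For each guess you will be prompted to select the number of points you would like to bet on your guess being correct". The menu is short ("i.e., 10, 25, or 50 points) on how other players will answer"). Rounds 7 and 8 are listed as exceptions to ordinary play, and there the Replay Bonus is described as "placing very large bets on a topic they already received feedback on and very small bets for topic on which feedback has not yet" been given. No point values are stated, and the text does not say whether the app or the player sets the amount.
- **Feedback.** In Rounds 3 and 4 the doors of evaluation study participants are fixed to their assigned sequence: "alcohol+coping, alcohol+control, or control only".
- **Follow-up.** For the trial, "answers to REPLAY BONUS questions in Round 7 among intervention study participants' will act as the 2 month post-intervention follow-up". Appendix C labels two topics for that bonus: "Alcohol Use Questions (Round 3 & Replay Bonus in Round 7") and "Stigma Questions (Round 3 & Replay Bonus in Round 7").
- **Measure.** The feedback screens present the player's "guess about how other players answered (i.e., perceived peer norm"), so the quantity that carries the bet is also the perceived-norm measure.

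**The concern.** Personalized normative feedback is meant to work by correcting what women believe about peer drinking. Section 4 expects benefit because participants learn that peers drink less than they had supposed. Section 3, Competition Conclusion, justifies the fixed doors by the wish to study perceptual as well as behavioral effects. Perceived alcohol norms are therefore the natural measure of mechanism.

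Points depend on the accuracy of the guess and decide cash prizes, so the stake is an incentive to be accurate or to recall a figure already shown. If that incentive is larger in the alcohol arms by construction, a Round 7 difference from control only does not show by itself that beliefs changed. Adjusting for the Round 3 guess does not help. At Round 3 every arm bets before any alcohol feedback, so the stake difference exists only at follow-up.

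**Working it through.** The protocol gives no figure to reproduce here, so the check is a trace through the text, some counts, and one illustration on assumed values.

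**1. From arm to stake**

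| Arm | Alcohol feedback before Round 7 | Round 7 alcohol stake if tied to feedback |
|---|---|---|
| Alcohol + coping | yes | very large |
| Alcohol + control | yes | very large |
| Control only | no | very small |

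Appendix C lists the alcohol questions for Rounds 3 and 7 only, and the Round 3 doors are fixed. Women in control only therefore have no other scheduled alcohol feedback before Round 7.

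**2. Contrasts affected.** Three arms give 3 pairwise contrasts. Two of them set an alcohol arm against control only. In the third, alcohol + coping against alcohol + control, the alcohol stake is the same on both sides.

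**3. Topics affected.** Appendix C lists 2 Replay Bonus topics for Round 7, alcohol and stigma. Stigma is named in none of the three feedback sequences. Alcohol is therefore the 1 listed topic of 2 whose stake would follow arm.

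**4. Is there a bet-free repeat?** The alcohol items in Appendix C are days per week, drinks per occasion, peak drinks and number of consequences, which makes 4 peer guesses. The post-competition survey in Appendix D has 5 drinking items: the same four subjects plus drinking to cope. All 5 ask about the woman herself, so 0 of 5 repeat a peer guess. The Round 4 item on peers who drink to cope is a coping norm and is listed for Round 4 only.

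**5. Two readings of the stake**

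- *Set or capped by the app according to prior feedback.* The stake is then a second difference between arms, delivered at the moment of measurement. The contrast estimates feedback plus stake.
- *Chosen by the player from a menu common to all arms.* A larger bet then reflects greater confidence after feedback and lies on the path from treatment to guess. The contrast is a valid total effect of feedback.

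**6. Illustration, first reading only.** Assumptions not in the protocol: equal allocation, two-sided 5% test, outcome SD 1, and a stake that shifts the reported guess by d SD while feedback itself has no effect. With 500 participants, n = 500/3 ≈ 167 per arm. At 80% retention, n = 500 × 0.8/3 ≈ 133.

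Rejection rate = Φ(d/SE − 1.96) + Φ(−d/SE − 1.96), with SE = √(2/n).

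For n = 167, SE = √(2/167) = 0.109. At d = 0.1, d/SE = 0.914, and the rate is Φ(−1.046) + Φ(−2.874) ≈ 0.148 + 0.002 = 0.150.

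| Assumed shift d (SD) | One alcohol arm vs control, n = 167 | n = 133 |
|---|---|---|
| 0 | 5% | 5% |
| 0.1 | 15% | 13% |
| 0.2 | 45% | 37% |
| 0.3 | 78% | 69% |

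The table shows only how sensitive the contrast would be if such a shift existed. It is not evidence that one exists. With one common stake d is 0, which is the first row.

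**The case against.** Four objections deserve an answer.

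**Players may set their own bets.** The Replay Bonus wording is permissive, players are its actors, and ordinary rounds have them select their points. On that reading nothing is confounded. This stands, and it is why the point is conditional. A reader might infer that bet size follows randomized arm as a matter of design. The text does not go that far, because it never says who sets the stake. Participants may also skip results screens (section 4), so even an app-set stake might not match assigned arm exactly.

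**The follow-up may mean own answers only.** Elsewhere the protocol separates a player's own answers from her guesses. But the items that Appendix C prints under the Round 7 Replay Bonus label are themselves peer-norm questions, with own-behavior questions run in parallel, and a bonus scored on bets needs the guesses. This objection does not remove the point.

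**Perceived norms are not the efficacy focus.** Correct. Section 1 puts efficacy on changes in alcohol use and coping behaviors. A reader might infer that the own-drinking results are biased too. The documents do not support that: the bets are placed on guesses about others, and own drinking is asked again without bets in Appendix D. The reach is limited to the perceptual question.

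**No bias has been sized.** Also correct. Women in control only have seen no alcohol norm, so a larger stake might not move their guesses, and every arm already has some incentive to be accurate.

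**Conclusion.** The point holds conditionally. If Replay Bonus stakes are set or capped by prior feedback, the Round 7 alcohol guesses in 2 of the 3 pairwise contrasts are made under unequal incentives, and those guesses are the only documented follow-up of perceived alcohol norms. A difference could not then be attributed to feedback alone. If players choose from a common menu, the total effect of feedback is still validly estimated. The protocol leaves open which reading applies.

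The direction and size of any bias are unknown, and the illustrative rates rest wholly on assumed shifts. The point does not threaten the own-drinking result or the comparison of the two alcohol arms. It is worth acting on because the repair is specific, nearly free, and settles the matter under either reading.

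**What to change.** In section 3, Replay Bonus Rounds 7 and 8, state that the Round 7 alcohol items carry the same fixed stake, or no bet, for all evaluation study participants regardless of prior feedback. Keep feedback-dependent betting for topics that are not trial outcomes.

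This takes one added sentence and one bet setting for one topic in one round. The downside is slightly less of the replay mechanic for alcohol in Round 7. Equal stakes do not abolish the incentive to recall a figure already shown, but they make the stake the same in every arm.

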4. RISKS / BENEFITS

What are the potential benefits to subjects and/or to others?

What are the reasonably foreseeable risks to the subjects? (Risks may include discomfort, embarrassment, nervousness, invasion of privacy, etc.) If there are potential risks to subjects, how will they be minimized in advance? How will problems be handled if they occur?

Participants will benefit from LezParlay through their receipt of detailed feedback revealing actual LBQ community norms and how they compare to LBQ peers on a wide range of behaviors and attitudes of interest to this population. Feedback on alcohol use and coping behaviors are anticipated to show participants that their peers consume less alcohol and drink to cope with negative affect less than they thought. This information is anticipated to have a protective effect on participants' own alcohol use. For

some, participation in LezParlay may also satisfy curiosities about the LBQ community or help to diminish harmful stereotypes. For others, learning about health and relationship behaviors of LBQ peers may benefit their own health behaviors and relationships. Others may simply find entertainment in the wagers, scoring and feedback. Participants' responses to LezParlay questions, in aggregate may also help shape future programming by our community partners, which in turn, may benefit their future well-being. In addition, participants in the evaluation study may enjoy the opportunity to share what they liked about LezParlay, what they hated, and any ideas they have for improvements with the game's founders.

Psychological risks posed by the research are primarily related to the sensitivity of some of the questions. Participants will be prompted to report their alcohol use, coping behaviors, health behaviors, future plans, relationship and sexual behaviors, information that may be private. These questions may make subjects uncomfortable or be perceived as an intrusion on their privacy. To mitigate these risks, all LezParlay question responses will be linked to unidentifiable PIN numbers and participants will be able to skip questions they do not feel comfortable answering without penalty. Participants may also experience discomfort upon receipt of personalized normative feedback. For example, it may be distressing for a participant to learn that other lesbians the same age are drinking much less but exercising much more than you. Although igniting such dissonance, or discomfort, is the primary goal of PNF interventions in that these feelings motivate healthy behavior change, participants will be provided an opportunity to skip the detailed results screens that provide PNF and advance to the next round if they wish to do so.

5. CONFIDENTIALITY

Will subjects be identifiable by name or other means? If subjects will be identifiable, explain the procedures that will be used for collecting, processing, and storing data.

Who will have access to data? What will be done with the data when the study is completed? If you are collecting visual images of your subjects please justify this.

Participants will not provide their full names and identifiable data will only be collected in the initial registration survey (their initials or a nickname, email address, mobile phone number, birthdate, relationship status, sexual identity, and a profile picture if they wish to upload one). The app's terms of Service and Privacy Policy clarify that displaying a profile photo, describing oneself via descriptive text, and entering all profile information with the exception of sexual identity and age group (required for round formatting) is optional and not required to take part in the LezParlay competition. It will also be clear that player's contact information entered at registration (email, phone) will not be visible to other players. It is important to emphasize that although participants will be able to browse one another's player profiles, no distinction will be made as to who is playing as an intervention study participant versus a non-study participant. Thus, while players may recognize one another when viewing profiles, participation in the evaluation study entirely remains confidential.

Submitting the registration form will trigger a verification text message to be sent to the mobile phone number provided by the participant. Upon receiving the text and clicking on the unique url delivered, the user will be updated with a verification checkmark in the registration database. Simultaneously, verification locks the phone number so that it cannot be associated with any future LezParlay registrations and assigns a unique PIN to the user in the registration database. As most individual's only own a single mobile phone (or 2 at the most), this protocol reduces players' ability to cheat in LezParlay by creating multiple accounts in order to place wagers on all possible combinations of guesses. Further, the unique PIN assigned to each verified account then acts as the piece of data used by LezParlay to link participants' guesses, bets, responses and scores across rounds of play.

As the LezParlay collects all round data through styled Qualtrics surveys fully embedded into the app, all data is protected by Transport Layer Security (TLS) encryption (also known as HTTPS), which is a protocol that ensures privacy between communicating applications and their users on the Internet. Also used to secure bank and credit card transactions online, TLS ensures that no third party may

eavesdrop or tamper with submitted data. Further, after data collection concludes and all personalized feedback, scores, and incentives, have been received by participants, user photos and identifying information will be destroyed. Only datasets containing de-identified LezParlay Round data will be downloaded from Qualtrics for analysis, password protected, and stored securely on HeadsUp's internal, further password protected server. Thus, these double password protected files will only be accessible to the PI ([name]) and Project Director ([name]).

6. INFORMED CONSENT

Attach an informed consent form or a written request for waiver of an informed consent form. Include waiver of written consent if appropriate. If your research is being conducted in another language, please include copies of the translated "Informed Consent" or "Waiver of Written Consent" forms.

This research requires 2 levels of consent. First, the LezParlay Terms of Service and Privacy Policy must be accepted by ALL players at sign-up. Second, players who meet Evaluation Study criteria during Round 3 and express interest in taking part in the study will be directed to review and complete the Evaluation Study's informed consent form. These documents are separately attached.

